#### 4. Analytic Methods to Meet the Primary and Exploratory Objectives

##### 4.1. Treatment

In the persistent AF analysis the subject device group is the ThermoCool ST catheter and the comparison group is the ThermoCool STSF catheter. In the ischemic VT analysis the subject device group is the ThermoCool STSF catheter.

##### 4.2 Covariates

For persistent AF an extensive list of covariates was considered. In 4.2.1 the original list is displayed. However, in some instances there was evidence of a positivity violation (i.e., there are

no observations in one of the device arms for at least one of the levels of a nominal covariate) or a value for a covariate was present for all patients in the data. All modifications to the original covariates for these reasons are described as notes to the tables provided in the Appendix.

#### 4.2.1 Persistent AF Covariates

Covariates ***included in the propensity score model:***

- Calendar year of procedure (2014-2018, 2019-2021)
- Patient Age (<65, 65-74, ≥75 years; based on CHA2DS2-VASc categories)
- Patient sex (male, female)
- Race (white, non-white)
- Hospital bed size (<500, ≥500)
- Number of AF ablations performed by cardiac electrophysiologists in prior 12 months (<25, 25-50, >50)
- History of valve replacement (no, yes)
- Mitral valve stenosis (no, yes)
- PCI (no, yes)
- CABG (no, yes)
- BMI\* (the latest prior to the index procedure) (continuous variable)
- Anemia (no, yes)
- Hypertension (no, yes)
- Diabetes mellitus (both type 1 and type 2) (no, yes)
- Obstructive sleep apnea (no, yes)
- Vascular disease history (prior MI or peripheral arterial disease or aortic plaque) (no, yes)
- Congestive heart failure (no, yes)
- Chronic pulmonary disease (no, yes)
- Ischemic stroke or hemorrhagic stroke or transient ischemic attack or thromboembolism (no, yes)
- Implantable cardioverter defibrillator or pacemaker (no, yes)
- Hospitalizations: AF related (no, yes)
- Chronic renal disease (stages 3-5) (no, yes)
- Elixhauser comorbidity index (≤3, >3)
- Electrical cardioversion (direct current cardioversion) for AF (no, yes)
- History of supraventricular arrhythmia (no, yes)
- History of ventricular arrhythmia (no, yes)
- Use of class I or III AAD (no, yes)
- Use of class II or IV AAD (beta blocker, calcium channel blocker) (no, yes)
- Use of anticoagulants (no, yes)
- Use of antiplatelets (no, yes)

Note: Demographic information, procedural characteristics, hospital and provider characteristics are recorded at the time of the index procedure. Medications are based on 6 months prior to the index procedure. Medical history, arrhythmia-related information and clinical characteristics use all available information prior to the index procedure unless otherwise specified. \* Recorded BMI or calculated BMI based on weight and height (weight in kg/height in m^2), the latest measurement prior to the index ablation procedure. AAD: antiarrhythmic drugs; AF: atrial fibrillation;

BMI: body mass index; CABG: coronary artery bypass grafting; MI: myocardial infarction; PCI: percutaneous coronary intervention

## 4.3 Endpoint Creation

### 4.3.1 Composite Safety Endpoint for Persistent AF

The composite safety endpoint for the persistent AF cohort will include several adverse events for patients undergoing ablation procedures. Adverse events evaluated within 7 days of the index procedure include:

- Death
- Acute MI
- Acute stroke/cerebrovascular accident
- Transient ischemic attack
- Thromboembolism
- Heart block
- Pericarditis
- Diaphragmatic paralysis
- Pneumothorax
- Pulmonary edema
- Major vascular access complication or bleeding requiring transfusion

Adverse events evaluated within 30 days of the index procedure include:

- Cardiac tamponade/perforation

Adverse events evaluated within 90 days of the index procedure include:

- Pulmonary vein stenosis
- Atrioesophageal fistula

The composite safety endpoint for persistent AF is a **time-to-event** outcome, given the longer follow-up for some events that make up the composite endpoint. If a patient experienced any of the safety events within the specified time-period for each event, they will be recorded as experiencing the composite safety endpoint. The event time will be the number of days from the index procedure to the date of the *earliest* safety event.

If *no* safety events occurred within the specified time-period for each event then patients will be censored and recorded as not experiencing the composite safety endpoint. For these patients censoring time will be measured as the number of days from the index procedure to the date of the *earliest* of three censoring events:

- i) Incomplete follow-up due to patient drop-out. This censoring event will be based on absence of a health care encounter documented in the EHR after 7 days of the index procedure. Censoring time corresponding to this censoring event is 7 days.
- ii) Incomplete follow-up for an administrative reason. This censoring event will be present if the latest date of follow-up - date of index procedure < 90 days. The latest date of follow-up

is determined by the date the data is extracted from the EHR. Censoring time for this censoring event can range from 0 to 89 days.

iii) End of follow-up period. Censoring time is 90 days.

#### 4.3.2 Composite Safety Endpoint for Ischemic VT

The composite safety endpoint for ischemic VT will include the following adverse events for patients undergoing procedures that occurred within 7 days of the index procedure:

- Death
- Acute MI
- Acute stroke
- Deep venous thrombosis
- Pulmonary embolus
- Complete heart block
- Pericardial effusion with hemodynamic compromise
- Cardiac perforation
- New acute severe mitral or aortic regurgitation
- Arterial dissection
- Vascular injury

The composite safety endpoint for ischemic VT is a binary outcome variable, given the short length of follow-up for all events. If a patient experienced any of the safety events within 7 days, they will be recorded as experiencing the composite safety endpoint. If *no* safety events occurred within 7 days then patients will be recorded as not experiencing the composite safety endpoint.

#### 4.3.3 Composite Effectiveness Endpoint for Persistent AF

A composite endpoint will be used in order to evaluate effectiveness for persistent AF over two time periods: through 6 months and through 1 year (after the index date). A 3-month blanking period (healing and stabilization) for persistent AF will be implemented for the assessment of effectiveness outcomes across groups.

The composite endpoint for AF consists of any of the following events after 3 months:

- Rehospitalization for atrial tachyarrhythmia (including AF, atrial tachycardia [AT], and atypical atrial flutter [AFL])
- Rehospitalization for heart failure
- Electrical cardioversion for AF/AT/AFL
- Repeat ablation for AF/AT/AFL

If a patient experienced any of the effectiveness events within the specified time-period, they will be recorded as experiencing the composite effectiveness endpoint. The event time will be the number of days from the index procedure to the date of the *earliest* effectiveness event.

If *no* effectiveness events occurred within the specified time-period for each event then patients will be censored and recorded as not experiencing the composite effectiveness endpoint. For

these patients censoring time will be measured as the number of days from the index procedure to the date of the *earliest* of four censoring events:

- i) Incomplete follow-up due to patient drop-out. This censoring event will be based on absence of a health care encounter documented in the EHR after 90 days from the index procedure. Censoring time corresponding to this censoring event is 90 days.
- ii) Incomplete follow-up for an administrative reason. This censoring event will be present if the latest date of follow-up - date of index procedure < 183 days. The latest date of follow-up is determined by the date that the data is extracted from the EHR. Censoring time for this censoring event can range from 0 to 182 days.
- iii) Death. This censoring event will be present if the date of death - date of index procedure < 183 days. Censoring time for this censoring event can range from 0 to 182 days.
- iv) End of follow-up period. Censoring time is 183 days.

\*Note: When the effectiveness endpoint is calculated for effectiveness at 1 year, 182 and 183 will be substituted with 364 and 365, respectively. Descriptive analysis will be performed to evaluate patients' characteristics with and without at least one-year in-person follow-up data (including both face-to-face visits and remote contact, such as telephone visits) for the exploratory effectiveness evaluation to assess any potential selection bias.

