#### 4.3.4 Composite Effectiveness Endpoint for Ischemic VT

A composite endpoint will be used in order to evaluate effectiveness for ischemic VT through 6 months and through 1 year (after the index date).

The composite endpoint for ischemic VT consists of any of the following events after the index procedure:

- Rehospitalization for VT
- Rehospitalization for heart failure
- Repeat ablation for VT

If a patient experienced any of the effectiveness events within the specified time-period, they will be recorded as experiencing the composite effectiveness endpoint. The event time will be the number of days from the index procedure to the date of the *earliest* effectiveness event.

If *no* effectiveness events occurred within the specified time-period for each event then patients will be censored and recorded as not experiencing the composite effectiveness endpoint. For these patients censoring time will be measured as the number of days from the index procedure to the date of the *earliest* of four censoring events:

- i) Incomplete follow-up due to patient drop-out. This censoring event will be based on absence of a health care encounter documented in the EHR after 7 days from the index procedure. Censoring time corresponding to this censoring event is 7 days.
- ii) Incomplete follow-up for an administrative reason. This censoring event will be present if the latest date of follow-up - date of index procedure < 183 days. The latest date of follow-up is determined by the date that the data is extracted from the EHR. Censoring time for this censoring event can range from 0 to 182 days.

- iii) Death. This censoring event will be present if the date of death - date of index procedure < 183 days. Censoring time for this censoring event can range from 0 to 182 days.
- iv) End of follow-up period. Censoring time is 183 days.

\*Note: When the effectiveness endpoint is calculated for effectiveness at 1 year, 182 and 183 will be substituted with 364 and 365, respectively. Descriptive analysis will be performed to evaluate patients' characteristics with and without at least one-year in-person follow-up data (including both face-to-face visits and remote contact, such as telephone visits) for the exploratory effectiveness evaluation to assess any potential selection bias.

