#### 4.4 Missing Data

Missing data on the outcomes can occur due to loss to follow-up. These patients will be censored at the time at which follow-up terminated. Missing data on the treatment variable is addressed in the study inclusion criteria. For missing covariate information an informative missing data approach is adopted, such that for nominal variables we create a separate level to indicate a missing value, and for continuous variables the mean is imputed and indicator variable for missing values on that variable is created [2]. The variables with levels representing missing data and missing data indicator variables were included in the propensity score model unless there was a positivity violation (i.e., there are no observations in one of the device arms with missing data on a particular covariate).

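### One encounter after day 7 or day 90 credits event-free follow-up to the full horizon, which sits badly with 4.4; effectiveness also censors death, and AF safety leaves deaths on days 8-90 unassigned

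*SAP*

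**What the plan says.** SAP 4.3.3 (persistent AF effectiveness) lists four censoring events and takes the earliest. Drop-out is the first: "This censoring event will be based on absence of a health care encounter documented in the EHR after 90 days from the index procedure", with censoring at day 90. The others are administrative censoring, death before the horizon, and the horizon itself: "End of follow-up period. Censoring time is 183 days". Administrative censoring does not use last contact: "The latest date of follow-up is determined by the date that the data is extracted from the EHR". For the 1-year endpoint the note says only that "182 and 183 will be substituted with 364 and 365, respectively", so the day-90 landmark stays.

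SAP 4.3.4 (ischemic VT effectiveness) has the same structure with an earlier landmark: "This censoring event will be based on absence of a health care encounter documented in the EHR after 7 days from the index procedure", censored at day 7.

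SAP 4.3.1 (persistent AF safety, the primary endpoint) defines drop-out as "absence of a health care encounter documented in the EHR after 7 days of the index procedure", censored at day 7; otherwise follow-up runs to extraction or day 90. Death within 7 days is an event. Death on days 8-90 is neither an event nor one of the three censoring events, yet the Table 2 shell counts deaths after day 7 under incomplete follow-up.

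SAP 4.4 gives the general rule for loss to follow-up: "These patients will be censored at the time at which follow-up terminated".

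SAP 1.2 makes effectiveness exploratory, without hypothesis tests. The notes in 4.3.3 and 4.3.4 plan a descriptive comparison of patients with and without one year of follow-up.

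**The concern.** The drop-out rule asks whether any encounter follows an early landmark, and puts no upper date on that encounter. It cannot recognise a patient who leaves the health system after the landmark. Such a patient stays in the risk set to the horizon while events treated elsewhere go unseen. Stretching the horizon from 183 to 365 days without moving the landmark widens the gap. A programmer following 4.4 and one following 4.3 could assign different censoring times to the same patient.

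Two further points concern death. In both effectiveness endpoints it is censored, although a patient who has died can no longer have the event. In AF safety, a patient seen on day 10 who dies on day 20 would, read literally, remain event-free and at risk to day 90.

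At stake are the 6-month and 1-year effectiveness risks and the descriptive ST versus STSF difference, and to a small degree the primary AF safety estimate.

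**Working it through.** The SAP states no figure for loss to follow-up, encounter frequency, mortality or effectiveness incidence, so there is none to reproduce. Every rate below is an assumption; the days are the SAP's.

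**1. Largest unobserved time the rule can credit** (horizon minus the first day after the landmark)

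| Endpoint | Last encounter | Horizon | Credited, unobserved |
|---|---|---|---|
| AF safety | day 8 | 90 | 90 - 8 = 82 days |
| AF effectiveness | day 91 | 183 | 183 - 91 = 92 days |
| AF effectiveness | day 91 | 365 | 365 - 91 = 274 days |
| VT effectiveness | day 8 | 183 | 183 - 8 = 175 days |
| VT effectiveness | day 8 | 365 | 365 - 8 = 357 days |

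**2. Direction.** Two effects oppose each other.

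- Credited but unobserved time keeps leavers in the denominator while their later events are missed. This lowers incidence.
- A captured event is itself an encounter. Patients censored at the landmark are therefore, by construction, those with no captured event afterwards. Removing them raises incidence.

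**3. Simulation of the rule with Kaplan-Meier.** There are 60,000 patients per scenario and no deaths. Exit from the system is 0, 10, 20 or 30% per year; the mean gap between routine encounters is 60, 180 or 365 days; events are captured only before exit; AF events occur only after day 90. Selected AF results at 1 year, true risk 30%:

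| Exit per year | Mean gap (days) | SAP rule, extraction at 3 years | Last-encounter censoring, 3 years | SAP rule, extraction at 400 days | Last-encounter censoring, 400 days |
|---|---|---|---|---|---|
| 0% | 60 | 30.0% | 30.0% | 30.0% | 33.6% |
| 0% | 365 | 30.7% | 31.0% | 42.2% | 59.7% |
| 30% | 60 | 28.3% | 31.6% | 28.0% | 34.8% |
| 30% | 180 | 30.4% | 33.7% | 32.9% | 47.7% |
| 30% | 365 | 33.2% | 36.1% | 41.8% | 61.6% |

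Over all scenarios the SAP rule gives 28.3-33.2% (3 years) and 28.0-42.2% (400 days). Last-encounter censoring gives 30.0-36.1% and 33.6-61.6%. With 3-year extraction the SAP rule gives 15.0-17.4% for AF at 6 months (true 15%) and 31.3-37.3% for VT at 1 year (true 35%). Censoring at the true exit date recovers the true value within about half a point throughout, which also indicates the simulation noise.

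**4. Death censored.** With constant hazards, let R be the 1 minus Kaplan-Meier risk and m the 1-year mortality. Then a = -ln(1 - R), b = -ln(1 - m), and the cumulative incidence is a/(a + b) × [1 - (1 - R)(1 - m)].

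- R = 30%, m = 2%: 0.3567/(0.3567 + 0.0202) × (1 - 0.70 × 0.98) = 29.7%; excess 0.3 points.
- R = 30%, m = 5%: 0.3567/(0.3567 + 0.0513) × (1 - 0.70 × 0.95) = 29.3%; excess 0.7 points.
- R = 35%, m = 10%: 0.4308/(0.4308 + 0.1054) × (1 - 0.65 × 0.90) = 33.3%; excess 1.7 points.
- R = 35%, m = 20%: 0.4308/(0.4308 + 0.2231) × (1 - 0.65 × 0.80) = 31.6%; excess 3.4 points.

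Section 4.7 sets out 1 minus Kaplan-Meier for persistent AF at 90 days only. Its use for effectiveness is inferred from the event and censoring times in 4.3.3 and 4.3.4.

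**5. AF safety.** After day 7 only tamponade/perforation (to day 30), pulmonary vein stenosis and atrioesophageal fistula (to day 90) can count. The drop-out rule and the unassigned deaths can act on these components alone.

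**The case against.** The best defence is that 4.3 is the specific rule and 4.4 the general one, so the landmark simply defines when follow-up ended. Table 2 supports this for AF safety, since it defines loss to follow-up by the same absence of encounters. Section 4.4 never mentions the last documented encounter, and a reader should not infer that it requires censoring there. This makes the conflict one of wording to be reconciled. It does not remove it: day 365 is hard to describe as the end of follow-up for someone last seen on day 91.

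Three stronger readings are tempting and are not supported.

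- *The rule biases incidence downward.* A reader might compute 0.30 × (1 - f/2), giving 28.5%, 27.0% and 25.5% when f = 10%, 20% and 30% of patients leave. That carries every leaver to the horizon and ignores the landmark censoring of patients with no later encounter. The rule as written can err either way.
- *Procedure era distorts the catheter comparison.* At Mercy 93.5% of ST but 24.1% of STSF procedures fall in 2014-18, and earlier patients have longer to produce a qualifying encounter. Those are unweighted figures. Under the chosen weights the absolute standardized difference for index year is 0.059 (Mercy) and 0.115 (Mayo). Differences within the two broad year bands are possible, but the SAP does not show them.
- *Last-encounter censoring is the cure.* It also depends on future encounters, and in the table above it can be further from the truth than the current rule.

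It also stands that effectiveness is exploratory, that success in Section 5 rests on safety, and that a descriptive selection check is planned. That check compares patient characteristics; it does not correct the estimates.

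**Conclusion.** The point holds as one of specification. Drop-out after the landmark cannot be recognised, the landmark is not scaled to the 1-year horizon, and 4.3 and 4.4 need reconciling. The exploratory risks are open to bias whose sign and size depend on encounter frequency, exit and extraction date. Under the assumed rates it runs from about 2 points below a true 30% to about 3 above with 3-year extraction, and to about 12 above with 400-day extraction and sparse encounters.

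Separately, censoring death overstates effectiveness incidence by a few tenths of a point at low mortality and by 1.7-3.4 points at an assumed 10-20%. This acts upward, so it cannot be added to a claim of downward bias.

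The disagreement between 4.3.1 and Table 2 on deaths on days 8-90 touches the primary AF endpoint, but the effect is probably small because only three components count after day 7. Study success is little affected, and nothing here shows that the primary safety conclusion would change.

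**What to change.** 1. Estimate 6-month and 1-year effectiveness with the Aalen-Johansen estimator, with death as a competing event. In the AF comparator arm, apply the same trimmed weights.
2. Reconcile 4.3 with 4.4 through one dated definition of end of observation that does not use future encounters, applied consistently at both horizons. One possible form treats a patient as observed until a pre-specified interval has passed since the most recent encounter. Report the current landmark rule and last-encounter censoring as sensitivity analyses, and present neither as unbiased.
3. Reconcile 4.3.1 with Table 2 on deaths after day 7, handling them as in effectiveness: as a competing event, not as plain censoring.

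The cost is SAP wording and modest programming on data already held. Any end of observation based on encounters may still be informative, so the sensitivity analyses remain necessary.

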#### 4.3.4 Composite Effectiveness Endpoint for Ischemic VT

A composite endpoint will be used in order to evaluate effectiveness for ischemic VT through 6 months and through 1 year (after the index date).

The composite endpoint for ischemic VT consists of any of the following events after the index procedure:

- Rehospitalization for VT
- Rehospitalization for heart failure
- Repeat ablation for VT

If a patient experienced any of the effectiveness events within the specified time-period, they will be recorded as experiencing the composite effectiveness endpoint. The event time will be the number of days from the index procedure to the date of the *earliest* effectiveness event.

If *no* effectiveness events occurred within the specified time-period for each event then patients will be censored and recorded as not experiencing the composite effectiveness endpoint. For these patients censoring time will be measured as the number of days from the index procedure to the date of the *earliest* of four censoring events:

- i) Incomplete follow-up due to patient drop-out. This censoring event will be based on absence of a health care encounter documented in the EHR after 7 days from the index procedure. Censoring time corresponding to this censoring event is 7 days.
- ii) Incomplete follow-up for an administrative reason. This censoring event will be present if the latest date of follow-up - date of index procedure < 183 days. The latest date of follow-up is determined by the date that the data is extracted from the EHR. Censoring time for this censoring event can range from 0 to 182 days.

- iii) Death. This censoring event will be present if the date of death - date of index procedure < 183 days. Censoring time for this censoring event can range from 0 to 182 days.
- iv) End of follow-up period. Censoring time is 183 days.

\*Note: When the effectiveness endpoint is calculated for effectiveness at 1 year, 182 and 183 will be substituted with 364 and 365, respectively. Descriptive analysis will be performed to evaluate patients' characteristics with and without at least one-year in-person follow-up data (including both face-to-face visits and remote contact, such as telephone visits) for the exploratory effectiveness evaluation to assess any potential selection bias.

